## 5.2 Recruitment, screening and baseline assessments

Brief Summary of Procedures (also see attached schedule of procedures and assessments):

Potential participants will be recruited from the community or they may be approached by collaborating clinicians or research team members (see recruitment plans) to explore potential participant's interest in taking part in a research study. Those who are interested will receive a telephone call from research staff to conduct a telephone screen. Those who pass the phone screen will receive an appointment to come to the research location to review and sign the informed consent form for screening purposes and to complete baseline diagnostic assessment screen, blood draw to test for CRP level, Hepatitis B and C, HIV, and rheumatoid arthritis, and will also complete an EKG to determine eligibility. Those who are eligible will return for a baseline visit and will review and sign another informed consent form for participation in the full protocol. Once fully consented, participants will undergo a series of visits to conduct multiple assessments which will include:

- (1) Psychological and Neuropsychological Tests at baseline and week 6; Open Label at week 6;
- (2) Medical Examination;
- (4) 3-4 Blood Collections (blood draw at screening, blood draw at baseline, blood draw at week 2 for liver function and hematocrit assessment, and one at Week 6) for those who enter the open-label phase they will receive an additional 2 blood draws (one at Open Label Week 2 to assess for liver function and hematocrit levels, and one at Open Label Week 6). All participants will be asked if willing to participate in additional blood collection for immune profiling.
- (5) 2-3 MRIs, one at baseline, one at week 6, and one at open-label week 6; the baseline scan will occur before treatment begins;
- (6) 2-3 fMRI (one at baseline which will occur during the same baseline MRI session, one at Week 6, and one at open-label week 6);
- (7) Optional Nutrition Assessment. Participants will be asked to do a 24-hour dietary recall. The food recall will also be collected using the Nutrition Data System for Research (NDSR). Participants are guided through a multiphase interview where they are guided to recall all the food they ate in the preceding 24 hours.
- (8) Participants will be closely monitored for problems resulting from participation. They will be provided with contact information for research personnel should any problems or questions arise, and they will be contacted by research personnel during their participation to ascertain the presence of any problem.

Treatment Design:

CONFIDENTIAL

All subjects will have an initial telephone screening. Screened participants will have an appointment to come to the research facility to conduct informed consent for the diagnostic screen and blood test to measure CRP levels and test for HIV, Hepatitis B and C, autoimmune diseases and rheumatoid factor. This visit is expected to last approximately 90 minutes. Informed consent will be obtained, and then participants will undergo a blood draw to assess c-reactive protein level, as they will be stratified depending on the current level. Subjects will participate in a structured clinical interview, EKG, and a review of medical history with the research staff. All participants will be given the screener for Structured Clinical Interview for DSM-IV (SCID-1) to ascertain the presence or absence of Major Depressive Disorder (MDD) and to rule out other psychiatric disorders. They will also be given the Hamilton Rating Scale for (HAMD) and Montgomery-Asberg Depression Rating Scale (MADRS). Those with MDD may be enrolled in the experimental condition. Potential Controls may be enrolled in the control condition if they have no psychiatric disorders and their HAMD score is less than or equal to 7. Participants will receive an EKG to screen for any abnormalities or conditions that would suggest they should not receive medication thus be deemed ineligible at this point. Participants will be asked medical screening questions (e.g., from the Framingham Scale to determine a vascular risk factor), and they will be assessed with the Clinical Dementia Rating (CDR) scale to determine whether there is any cognitive impairment. At the screening, the participants will be asked to fill out the Perceived Stress Scale (PSS) and Life Events Stress (LES). A trained study team member will then perform a neuropsychiatric test on the participants that include questions about the participants' memory, attention, spatial abilities, general abilities, motor control, and problem solving.

At this point, all participants who remain eligible will undergo a second informed consent to address the next steps in participation. Following the acquisition of the second consent, an appointment will be scheduled for the participant to conduct the baseline assessments. At these baseline assessments participants will receive their actigraph which will monitor their physical activity throughout the course of the study. These baseline assessments include neuropsychological tests, which will take approximately 1 hour to complete. Also at baseline, participants will receive anMRI (detailed further below).Following completion of all baseline assessments, the experimental group participants will receive the drug. Participants will take 10 mg of the antidepressant + placebo or 10 mg of the antidepressant + celecoxib for 3 days, and then they will increase the antidepressant to 20 mg for the remaining 39 days of the study. Final dose (10 mg versus 20 mg) will be determined by clinical response and side effects. This decision will be based on an ongoing discussion between the participant and the study doctor. Participants will be closely monitored for side effects via phone calls from research staff and in person inquiries during the follow-up visits. They will be provided with contact information (phone numbers) for research personnel should any problems or questions arise, and they will also be instructed to contact research personnel with any problems, questions, or concerns. Participants in the experimental group will have scheduled appointments at weeks 0, 1, 2, 4, and

CONFIDENTIAL

This material is the property of the University of Pennsylvania.

6. At the end of the 6 weeks participants will have their final physical and psychological assessment. Individuals remitting will be given an additional 2 weeks of escitalopram at this time; this is done so that individuals have enough time to schedule a visit with a provider of their choice, if they wish to remain on the medication. At the end of the study, all depressed participants will be transitioned into follow-up care with their own doctor or given a referral. For those who do not remit and had received escitalopram + placebo initially, they will be eligible for the open-label phase of the study. During this phase they will be given escitalopram + celecoxib. They will follow the same study procedures as the initial phase of the study (Medication visits Week 1, Week 2, Week 4, 3rd and Final MRI, neurocognitive testing, and blood draw).

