## Study Summary

Title	Stress and Inflammation in the Pathophysiology of Depression
Short Title	Stress and Inflammation
IRB Number	819654
Phase	Phase 4
Methodology	Double-blinded study or open-label; Randomized, placebo-controlled, one-phase study
Study Duration	This study will last 6-12 weeks, dependent on whether the participant enters the open-label phase of the study.
Study Center(s)	Single-center.
Objectives	1: Characterize neuroanatomical and neuropsychological correlates of abnormal cytokines in MDD. 2: Characterize the reversibility of brain dysfunction, including cognitive impairment, with treatment of depression and its association with inflammation.
Number of Subjects	100 depressed subjects, 50 control subjects
Main Inclusion and Exclusion Criteria	18-80, depressed, males and females, without psychosis or other concomitant psychiatric illnesses, or significant cardiac, liver, or GI disease.
Drugs	Escitalopram 10 mg/day for 3 days and then 20 mg/day for 39 day (taper down of 10 mg for 3 days) with placebo or Escitalopram 10 mg/day for 3 days and then 20 mg/day for 39 day (taper down of 10 mg for 3 days) with celecoxib (400 mg/day)

CONFIDENTIAL

Duration of administration	6-12 weeks
Statistical Methodology	The design of this trial is simple repeated measures design.
Safety Evaluations	This is a low-risk study. Subject safety will be closely monitored. Subjects reporting of side effects will be used to evaluate individual safety of high doses of escitalopram and celecoxib. Additionally, heart rate monitoring will allow us to assess the safety of celecoxib for blood pressure risks.
Data and Safety Monitoring Plan	The sponsor is responsible for monitoring the data quality and the ongoing safety of subjects. The PI will be monitoring the data quality and the ongoing safety of subjects.

CONFIDENTIAL

This material is the property of the University of Pennsylvania.

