**2.2 Study Design**

100 depressed and 50 control subjects, age 18-80, male and female, will be recruited for this study. Depressed participants will be stratified based on their c-reactive protein (CRP) levels (i.e., “High” CRP $\geq$ 3 and “Low” CRP<3). All participants will be started on either 10 mg of escitalopram + placebo or 10 mg of escitalopram + celecoxib (400mg/day) daily for 3 days. Following this lead-in dose of the SSRI they will then take 20 mg daily thereafter for 39 days and have no changes in their dose of placebo or celecoxib. Follow-up visits for all depressed participants will occur at 1 week, 2-weeks, and 4-weeks, following the start of treatment. The study coordinator and PI will monitor side effects and vital signs, and the PI may adjust the medication dosage depending on the patient's response to treatment and/or the presence of side effects. Final dose (10 mg versus 20 mg, or a dose between 10 mg and 20 mg, e.g., 15 mg) will be determined by clinical response and side effects. This decision will be based on an ongoing discussion between the participant and the study doctor. Participants who remit will have their end of study visit with a blood draw, and neuropsych testing at 6 weeks. Participants will then taper off medication at 10 mg for 3 days (if taking 20 mg during study). Based on past studies, less than 10% of participants will be taking less than 20 mg/day of SSRI at the end of the study.

Participants initially randomized to escitalopram + placebo, who do not remit will be treated with 6 weeks of escitalopram + celecoxib. They will not repeat the baseline visit, but will re-complete medication visits at week 1,2, and 4, After the 6 weeks of escitalopram + celecoxib they will undergo a 3rd MRI, neurocognitive session, and blood draw. Those who complete the study at this point will taper off medication at 10 mg for 3 days.

CONFIDENTIAL

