Participants will have total study participation of 6-12 weeks. Participants may have unscheduled visits occur throughout the course of the study (screening-completion), if participants are unable to complete the required assessments within the allotted time period. If this occurs participants will be compensated for the travel to these additional visits, but no changes will be made to their human subjects payment. Non-depressed, control group participants will not receive the study drug, and they will not attend the medication check visits at week 1, 2, and 4. Therefore, they will have 3-4 study visits: 1-2 screening visits, 1 baseline visit: blood draw, MRI, and neuropsych testing; Week 6 visit: blood draw, MRI scan, and neuropsych testing.

Participants will be recontacted six months post-study completion to assess efficacy and longevity of the treatment. At the six-month follow-up, participants will be asked to complete a series of questionnaires regarding their medical and psychiatric history. This follow-up appointment is optional.

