##### **4.2 Intervention Regimen**

Participants will take escitalopram (10 mg/day for 3 days and 20 mg/day for 39 days ) plus celecoxib (400 mg/day) or escitalopram (10 mg/day for 3 days and 20 mg/day for 39 days ) plus placebo for 6 weeks. Participants will be lowered to a smaller dose of the study drug, if they are unable to handle the higher dose (as determined by side effects or subjects expressing concerns about side-effects). All participants will receive a taper dose of escitalopram at 10 mg for 3 days at the completion of the study.

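### Sections 2.2 and 4.2 taper a week-6 remitter off escitalopram over 3 days, while section 5.2 gives the same participant 2 more weeks; the passages must be reconciled

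*Combined protocol and SAP*

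**What the plan says.** Section 2.2 places the remitter's last visit at week 6: "Participants who remit will have their end of study visit with a blood draw, and neuropsych testing at 6 weeks". It continues: "Participants will then taper off medication at 10 mg for 3 days (if taking 20 mg during study").

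Section 4.2 has the same taper without the dose condition: "All participants will receive a taper dose of escitalopram at 10 mg for 3 days at the completion of the study". The Study Summary lists it ("taper down of 10 mg for 3 days") in both regimens, with placebo and with celecoxib.

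Section 5.2, describing the end of the 6 weeks, says: "Individuals remitting will be given an additional 2 weeks of escitalopram at this time". The stated purpose is time to arrange a visit with a provider, "if they wish to remain on the medication". It then adds: "At the end of the study, all depressed participants will be transitioned into follow-up care with their own doctor or given a referral". Section 5.2 gives no dose for the extra supply and no taper after it.

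The flow chart in section 12.1 marks drug dispensing at week 6 but labels the row as weeks 0 to 6. It lists neither the taper nor the extra supply.

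On later follow-up, section 2.2 says: "Participants will be recontacted six months post-study completion to assess efficacy and longevity of the treatment". That contact is optional and consists of medical and psychiatric history questionnaires.

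**The concern.** The end of antidepressant treatment is a point where staff need one instruction. Here, two sections tell them to bring a newly remitted participant off escitalopram within days of the week-6 visit, and a third tells them to hand over 2 more weeks of it. Whoever works from sections 2.2 and 4.2 ends the supply before the window that section 5.2 creates for finding a provider has closed. Whoever works from section 5.2 omits a taper that section 4.2 gives to all participants.

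What is at stake is consistent handling of participants as they leave the study, and a record of what each was given. The estimates of treatment effect at week 6 are not at stake.

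**Working it through.** No power, sample-size or error-rate figure is involved. The check is a comparison of the passages and a day count.

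**Step 1: length of treatment.** Section 4.2 gives 3 days at 10 mg and 39 days at 20 mg. 3 + 39 = 42 days = 6 × 7, which agrees with the stated 6 weeks.

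**Step 2: last escitalopram dose for a week-6 remitter.** This assumes visits on schedule and the full supply taken.

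| Source | Participant on 20 mg | Participant on 10 mg |
|---|---|---|
| 2.2 | 42 + 3 = day 45 | no taper: day 42 |
| 4.2 | 42 + 3 = day 45 | 42 + 3 = day 45 |
| 5.2 | 42 + 14 = day 56 | 42 + 14 = day 56 |

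At 20 mg the gap is 56 − 45 = 11 days. If a 3-day taper were meant to follow the extra supply, which section 5.2 does not say, the last dose would be day 56 + 3 = 59 and the gap 59 − 45 = 14 days.

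**Step 3: below 20 mg.** Sections 2.2 and 4.2 both allow a lower dose. The taper in section 2.2 depends on taking 20 mg; the one in section 4.2 does not. For someone already on 10 mg, the taper in section 4.2 is 3 more days at the same dose. For someone on an intermediate dose such as 15 mg, which section 2.2 permits, section 4.2 gives a taper and section 2.2, read literally, does not. Section 2.2 expects less than 10% of participants to end below 20 mg, which is fewer than 10 if applied to all 100 depressed participants.

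**Step 4: does any passage resolve the conflict?** Section 5.2 gives the supply to remitters as a group; the wish to continue appears only in its stated purpose. Sections 2.2 and 4.2 do not exempt those who want to continue. The flow chart lists neither step. Nothing in the text links the two rules.

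**Step 5: which data are touched?** Both rules take effect after the week-6 assessment, so week-6 MADRS, IL-6, imaging and neuropsychological data are unaffected. The six-month contact is not among the outcomes in section 2.1 or the variables in section 6.2, and section 6 plans no analysis of it.

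**The case against.** The strongest reply is that the passages can be harmonised: the 2 weeks bridge those who may wish to continue, and the taper is for those who stop, or comes after the bridge. Staff could dispense both, so it would be wrong to call the instructions impossible to carry out together. That much stands. But the documents state neither arrangement, and staff would have to supply the rule themselves. It is also fair that referral or follow-up care is promised to all depressed participants under either rule; what differs is the drug supply while it is arranged.

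Several stronger readings are tempting, but the documents do not support them:

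- **A six-month outcome is compromised by pooling stopped and continued patients.** No six-month endpoint or analysis is defined, so nothing is pooled. A mix is likely, but mainly because section 5.2 leaves continuing to the participant and sends everyone to outside care. Reconciling the taper wording would not remove it.
- **Different sites would act differently.** The Study Summary says the trial is single-center. Only variation between staff remains.
- **Celecoxib-arm non-remitters have no adequate stopping instruction.** The Study Summary attaches the taper to the celecoxib regimen, and section 4.2 covers all participants.
- **About 47 remitters are affected, as 100 minus the 53 in section 6.1.** Section 6.1 speaks of randomizing those 53 between two groups in a second phase. The current open-label phase is not randomized and admits only placebo-arm non-remitters, at most 50 people by section 1.1. The 53 cannot be its intake, and the plan gives no number of remitters.

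**Conclusion.** The contradiction is real. For week-6 remitters on 20 mg, the Study Summary and sections 2.2 and 4.2 lead to a last dose at about day 45, and section 5.2 to about day 56: 11 days apart, or 14 if a taper follows the extra supply. The day counts assume on-schedule visits and use of the full supply; a participant who does not take all of it would show a smaller gap. A second, smaller conflict between sections 2.2 and 4.2 concerns participants below 20 mg. The number of participants affected cannot be derived from the documents.

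This is an internal inconsistency in end-of-treatment instructions that bears on participant care and on what is recorded at exit. It does not bias any listed outcome. This review takes no position on which rule is right.

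**What to change.** Reconcile the Study Summary, sections 2.2, 4.2 and 5.2 and the flow chart in section 12.1 into one end-of-treatment statement for each exit group: remitters in either arm, celecoxib-arm non-remitters, placebo-arm non-remitters who enter or decline the open-label phase, and open-label completers. State how it applies to participants below 20 mg. The sponsor and its clinicians choose the rule.

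Add a field to the week-6 case report form for what was dispensed at exit (taper, extra supply or both, and dose).

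If the six-month contact is to describe longevity of treatment, also record antidepressant use at that contact. The week-6 path alone does not show who is still on drug: a participant given the extra supply may stop at day 56, and a tapered one may restart with an outside provider.

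The cost is a wording amendment, one form field at week 6 and, if the follow-up is used, one questionnaire item. No visits or participants are added.

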### **5.3 Assessment measures and neuropsychiatric tests**

The following assessment measures and neuropsychiatric tests will be used:

Structured Clinical Interview for DSM-IV Axis I Disorders (SCID-I - Abbreviated version). The Structured Clinical Interview for DSM-IV Axis I Disorders (SCID-I) is a semi-structured interview for making Axis-I diagnoses according to the DSM-IV, and usually takes 60-90 minutes to administer. We will perform only the overview portion;

Montgomery-Asberg Depression Rating Scale (MADRS). The ten-item MADRS will be used to determine the presence of and severity of current depressive symptoms, and will be the primary outcome measure of depression severity in this study. The MADRS is included as it was used in our previous studies and will allow for comparison;

Hamilton Rating Scale for Depression (HAMD). All patients and controls will also be assessed using the HAMD, 17-item version, to determine the presence of any current depressive symptoms. The HAMD is included as it is more widely used in the US than the MADRS;

Montreal Cognitive Assessment (MOCA): This short test of visual and verbal functioning and delayed recall gives an indication of cognitive decline and dementia..

Framingham scale. For each subject we will rate a vascular risk factor (VRF) total score using the approach of the Framingham Study (Wolf et al., 1991), which gives a validated number based on the presence and severity of VRFs, weighted according to their predictive power for stroke;

Cumulative Illness Rating Scale-Geriatric (CIRS-G). A history of major illnesses and treatments will be taken, and the Cumulative Illness Rating Scale-Geriatric (CIRS-G) will be completed by the evaluating physician at the start of the trial (Miller et al., 1992). The CIRS-G covers all major systems (cardiovascular, pulmonary, renal, genitourinary, etc), and provides scores for current and past medical illnesses, including a global composite score that will be used as a measure of medical morbidity;

CONFIDENTIAL

The following Self-Report Questionnaires will be distributed:

Perceived Stress Scale (PSS). We will use the PSS score, a validated measure of subjective life stress to characterize the relationship between inflammatory cytokine levels, subjective stress, depression severity and treatment response. It is the most widely used measure of subjective stress;

Life Events Stress (LES) Scale. Each event is assigned a weight for the severity of the stressor, e.g. death of spouse vs. friction at work. Scores for all relevant events are summed to yield a total life events stress score. This scale will be used to determine the cumulative amount of stress experienced by each participant;

Maltreatment and Abuse Chronology of Exposure (MACE) Scale There is reason to believe that childhood maltreatment can affect the trajectory of brain development and enhance the risk of medical and psychiatric disorders. We will use this scale to further test this theory. The 'Maltreatment and Abuse Chronology of Exposure' (MACE) scale (1) can be used to assess not only the type and severity of abuse exposure but also the timing of the exposure. There is increasing interest in childhood maltreatment as a potent stimulus that may alter trajectories of brain development and enhance the risk for medical and psychiatric disorders. Although a number of other scales exist for retrospective assessment they fail to provide detailed information on the timing of the exposure, critical for delineation of sensitive periods. Using the MACE (2) both dose dependent and timing effects were demonstrated for some disorders, whereas overall amount of adverse experiences was the critical. In our current study the variables obtained from the MACE will be included in predictive models to help understand which brain circuits are affected in particular symptom clusters and disorders. This will help us improve our predictive models, given the strong relationships obtained using the MACE. Answers to the MACE will be anonymized and entered into the database. As with all procedures, participation is voluntary and it will be explained to participants that the interview might be uncomfortable or upsetting. In the event that a participant becomes upset they will be asked if they would like to stop the questions. Participants will be asked if they would like counseling and referred for care if appropriate.

The following comprises the Complete Neuropsychological Battery. This will be performed at the beginning and end (weeks 0 and 6):

Controlled Oral Word Association (COWA)/Verbal Fluency: In these tests, which are widely validated tests of frontal lobe function (Cohen, 1993), subjects are given 60 seconds to generate as many words as possible that begin with a specific letter of the alphabet or to name as many examples in a particular category (such as animals), respectively. Subjects receive one point for every correct word. For the COWA, a standardized set of letters (CFL) with established norms

CONFIDENTIAL

This material is the property of the University of Pennsylvania.

will be used. The animal category is the easiest of the verbal fluency categories (Monsch, 1992) and has been shown to discriminate Alzheimers Disease from depression, whereas letter fluency did not (Hart, 1988);

**Trail Making Test A&B:** In this test subjects are required to sequentially connect on a page of paper dots that are marked with either letters or numbers (Part A). They are then instructed to connect dots by alternating between numbers and letters sequentially (e.g. 1-A-2-B-3-C-4-) (Part B). In each part, performance is timed. This test is sensitive to deficits in visuomotor tracking, speed, and attention (Lezak, 1995), and performance is correlated with frontal activation (Segalowitz, 1992). Studies show depressed patients to be significantly slower on Part B (King, 1993). Normative studies show increased performance times with age;

**Mini-Mental Status Exam:** This is a short 5 minute test used to assess orientation, memory, and recall. It measures cognitive decline and dementia. Participants must score a 26 or above to participate in the study.

**Word List Memory Test:** In this test a 10-word list is presented to subjects three times and immediate free recall of the list is tested after each presentation. Then following a 30-minute delay, free recall is again tested. Subjects are then asked to recognize the learned words from a list of 20 words. This test measures immediate and long-term memory and allows for an assessment of both memory acquisition and retrieval;

**Digits Forward:** This simple test of memory and concentration subjects are presented orally with a list of digits and are required to recite them back to the examiner. The digit list becomes progressively longer. Subjects are scored based on the number of correct trials;

**Digits Backward:** This simple test of memory and concentration subjects are presented orally with a list of digits and are required to recite them in reverse order. The digit list becomes progressively longer. Subjects are scored based on the number of correct trials;

**Digits Ascending:** This simple test of memory and concentration subjects are presented orally with a list of digits and are required to recite them in ascending order. The digit list becomes progressively longer. Subjects are scored based on the number of correct trials;

**Logical Memory (Immediate and Delayed Recall):** This subtest of the Wechsler Memory Scale tests immediate recall. In this task a short story is read to the subject and they are required to recall the story immediately following the presentation. They are scored based on the number of correct elements recalled from the story. After a 30 minute delay the subject will be asked to recall each story again;

**Digit Symbol:** In this task, subjects are given a key in which symbols are assigned a digital value from 1-9. Subjects are then required to use the key to translate a list of symbols into digits;

CONFIDENTIAL

Benton Visual Retention Test: This task has the participants look at 10 cards, one at a time, for 10 seconds, the card is removed and they are to draw what they saw on the card;

Shipley Vocabulary Test: The subject is given a word along with 4 choices and asked to circle the word that means the same thing as the given word;

Boston Naming: The subject is shown cards and asked to name the picture that appears on the card;

Stroop Color and Word Test: This task has participants read a series words that spell out different colors in a color not the same as the word itself. This is a measure of selective attention and processing speed.

**MRI procedures:** At baseline, all participants will be taken to University of Pennsylvania imaging facilities for neuroimaging whereby MRI and a fMRI will be conducted. At baseline, we will acquire anatomical MR images as well as functional MR images while doing the resting state connectivity task. We will also acquire functional MR images at the end of the study (end of week 6).

**Image Acquisition:** Structural and functional scans will be obtained in a single session on a clinically-approved 3 Tesla Siemens Trio (Erlangen, Germany) scanner, equipped with 40mT/m gradients and 200 mT/m/s slew-rates. RF transmission will use a quadrature body-coil, and reception will use a Siemens receive-only 64-channel head coil. The total time in the scanner will be approximately 1 hour. Based on our experience, this is well within patients ability to tolerate the scanning procedures without discomfort and without excessive motion. We will acquire structural images, perfusion images, and functional images as follows; all MRI imaging be reviewed and approved by CAMRIS. **High-resolution Anatomical Images:** A 5 min. magnetization prepared, rapid acquisition gradient echo (MPRAGE) image is acquired, which includes an inversion recovery preparation period to produce T1-weighted contrast, and has a 1x1x1mm voxel size. The MPRAGE is used to screen for gross anatomical abnormalities, to facilitate registration of lower resolution functional images into a standardized space, and to allow identification of between-group or inter-individual variation in volume of regions that could affect interpretation of functional results.

**Resting Perfusion Images:** A ~5 min. pulsed arterial spin labeled (ASL) perfusion MRI and ~1.5 min. reference scan are acquired to directly measure resting cerebral blood flow, using magnetically-labeled blood as an endogenous non-invasive tracer. **Functional Images:** Functional scans lasting ~15 minutes. fMRI will be acquired with blood oxygenation level dependent imaging (BOLD) using a whole-brain, single-shot gradient-echo (GE) echo-planar (EPI) sequence. The BOLD sequences include on-line geometric correction for spatial distortions due to magnetic field inhomogeneity using a magnetic field map acquired with a 2 min reference scan.

CONFIDENTIAL

